6.1.1 Drug-Device Combination Products/Combination Medicinal Product

The investigational drug-device combination product/combination medicinal product provided for use in this study is MK-6194. Refer to Section 8.4.8 and Appendix 4 for reporting events.

6.2 Preparation/Handling/Storage/Accountability

6.2.1 Dose Preparation

There are no specific calculations or evaluations required to be performed to administer the proper dose to each participant. The rationale for selection of doses to be used in this study is in Section 4.3.

6.2.2 Handling, Storage, and Accountability

The investigator or designee must confirm appropriate temperature conditions have been maintained during transit for all study intervention received, and any discrepancies are reported and resolved before use of the study intervention.

Only participants enrolled in the study may receive study intervention, and only authorized site staff may supply or administer study intervention. All study interventions must be stored in a secure, environmentally controlled, and monitored (manual or automated) area in accordance with the labeled storage conditions with access limited to the investigator and authorized site staff.

The investigator, institution, or the head of the medical institution (where applicable) is responsible for study intervention accountability, reconciliation, and record maintenance (ie, receipt, reconciliation, and final disposition records).

For all study sites, the local country Sponsor personnel or designee will provide appropriate documentation that must be completed for drug accountability and return, or local discard and destruction if appropriate. Where local discard and destruction is appropriate, the investigator is responsible for ensuring that a local discard/destruction procedure is documented.

The study site is responsible for recording the lot number, manufacturer, and expiry date for any locally purchased product (if applicable) as per local guidelines unless otherwise instructed by the Sponsor.

The investigator shall take responsibility for and shall take all steps to maintain appropriate records and ensure appropriate supply, storage, handling, distribution, and usage of study interventions in accordance with the protocol and any applicable laws and regulations.

6.3 Measures to Minimize Bias: Randomization and Blinding

6.3.1 Intervention Assignment

Intervention randomization will occur centrally using an IRT system. There are 3 study intervention arms. Participants will be assigned randomly in a 1:1:1 ratio to MK-6194 3 mg Q2W, MK-6194 3 mg Q4W, or placebo during the Double-Blind Treatment Period.

During the Blinded Extension Period, participants who were assigned to the placebo arm during the Double-Blind Treatment Period will be rerandomized 1:1 to MK-6194 3 mg Q2W or MK-6194 3 mg Q4W and will be given new randomization numbers. Participants who were assigned to either of the MK-6194 arms during the Double-Blind Treatment Period will continue to receive 3 mg MK-6194 with the same dosing schedule; however, will be assigned new randomization numbers in order to maintain the study blind during the Blinded Extension Period.

In order to maintain the blind, all participants will self-administer study intervention Q2W. Participants in the 3 mg MK-6194 Q4W group will alternate between placebo and MK-6194.

If futility criteria are met at the IA in both treatment arms, the study will stop early. If futility criteria are met for one treatment arm, participants who complete the Double-Blind Treatment Period of the study, but have not started the Blinded Extension Period, will be switched to the nonfutile arm for the Blinded Extension Period.

If a dose arm is found to be subefficacious during the Week 24 primary endpoint analysis, participants in the Blinded Extension who are already part of the subefficacious dose arm may continue on that dose; however, there will be no new enrollment to the subefficacious dose arm (Section 9.6). Participants who are still receiving the subefficacious dose in the Double-Blind Treatment Period will finish the Double-Blind Treatment Period as randomized but will receive the efficacious dose in the Blinded Extension Period.

6.3.2 Stratification

Intervention randomization will be stratified according to the following factors:

1. Stable vs active vitiligo

Treatment response in active versus stable vitiligo might be different.

- Active vitiligo is defined as new/extending lesion(s) in the 6 months prior to Screening Visit (confirmed by photographs or medical record/history) and/or; confetti-like lesion(s); trichrome lesion(s); Koebner phenomenon/phenomena (excluding Type 1 [history based on isomorphic reaction]), inflammatory vitiligo.
- Stable vitiligo is defined as an absence of signs of active disease (no signs of new or extending lesions).

2. *Previous JAKi exposure (yes or no)*

- It is unknown whether exposure to JAKi may affect response to an IL-2 mutein or if an inadequate response to JAKi may predict an inadequate response to MK-6194.

6.3.3 Blinding

A double-blinding technique with in-house blinding will be used. MK-6194 and placebo will be packaged identically so that blind is maintained.

Clinical site personnel, participants, and most Sponsor personnel will remain blinded for the duration of the study (ie, through Week 54). Only selected Sponsor personnel involved in performing and reviewing the results of the Week 24 analyses will be unblinded at the time of the Week 24 database lock.

See Section 8.1.11 for the description of unblinding if a medical emergency occurs during the study.

6.4 Study Intervention Compliance

Interruptions from the protocol-specified treatment plan for ≥ 2 consecutive injections require consultation between the investigator and the Sponsor and written documentation of the collaborative decision on participant management.

When participants self-administer study intervention at the site (witnessed doses per SoA), compliance with study intervention will be assessed by site personnel observation. Alternatively, participants may receive study intervention directly from the investigator or designee. The date and time of each dose administered in the clinic will be recorded in the source documents, the CRF, and the Participant Reminder Log.

When participants self-administer study intervention away from the clinic, compliance with study intervention will be assessed at the following site visit. Participants will record the date and time of the administered dose on the Participant Reminder Log. Compliance will be assessed by direct questioning during review of the Participant Reminder Log and inspection of the returned study intervention syringe(s) (used and unused, when applicable) and documented in the source documents and CRF. Deviation(s) from the prescribed dosage regimen should be recorded in the CRF.

If a discrepancy is noted when comparing entries in the Participant Reminder Log with the amounts of returned study intervention, the investigator or qualified designee must discuss the discrepancy with the participant and the explanation must be documented. Only the participant is allowed to make any changes to the log entries. The investigator or qualified designee will be responsible for transferring the appropriate information from the log into the appropriate CRF.

A record of the number of prefilled syringes dispensed to and administered by each participant must be maintained and reconciled with study intervention and compliance records. Intervention administration dates will also be recorded in the CRF.

6.5 Concomitant Therapy

Prohibited Concomitant Medications

Medications or vaccinations specifically prohibited in the exclusion criteria are also prohibited during the study. Please refer to [Table 1](#) (in Section 5.2) for medications which are prohibited during the study until the last dose of study intervention. Live vaccines, except for JYNNEOS, are prohibited during the study until 6 weeks after the last dose of study intervention. See Appendix 8 for examples of live vaccines and Appendix 7 for country-specific requirements.

Any prescription or over-the-counter medication, traditional Chinese medicine, herbal supplement, or other therapy used to treat vitiligo (or could affect vitiligo) are prohibited during the study to avoid confounding of results.

If there is a clinical indication for any medications or vaccinations specifically prohibited, discontinuation from study intervention may be required. The investigator should discuss any questions regarding this with the Sponsor Clinical Director. The final decision on any supportive therapy or vaccination rests with the investigator and/or the participant's primary physician. However, the decision to continue the participant on study intervention requires the mutual agreement of the investigator, the Sponsor, and the participant.

Any medication or vaccine (including over-the-counter or prescription medicines, vitamins, and/or herbal supplements or other specific categories of interest) that the participant is receiving at the time of enrollment or receives during the study must be recorded along with:

- Reason for use
- Dates of administration including start and end dates
- Dosage information including dose, route, and frequency

The Sponsor Clinical Director should be contacted if there are any questions regarding concomitant or prior therapy.

Note: It is the responsibility of the investigator to ensure participants with concomitant medical conditions are treated according to local guidelines/standard of care.

6.5.1 Rescue Medications and Supportive Care

No rescue or supportive medications are specified for use in this study.

6.6 Dose Modification

There are no dose modifications in this study.

6.6.1 Management of Serious Adverse Event of Infection

Interrupt study intervention if a participant develops an SAE of infection. Study intervention may be restarted once the infection has been successfully treated, per investigator discretion.

6.6.2 Management of COVID-19 Infection

Interrupt study intervention if a participant has a confirmed diagnosis of COVID-19 infection. Study intervention may be restarted once the infection or symptom is resolved, per investigator discretion.

6.6.3 Management of Eosinophilia

For participants with AEC \leq 650 cells/ μ L at Screening:

- If AEC is >1000 cells/ μ L at a scheduled or unscheduled visit after Randomization, another CBC with differential must be performed before the next dose. It is recommended to perform the CBC with differential close to the next dosing day and at least 10 days after the prior dose.
- If AEC is still >1000 cells/ μ L, a CBC with differential may be repeated the day before the dosing day or on the dosing day, prior to administration of study intervention.
- If AEC remains >1000 cells/ μ L, study intervention should be interrupted. Study intervention may be restarted once AEC is ≤ 1000 cells/ μ L.

For participants with AEC >650 cells/ μ L at Screening:

- If AEC at a scheduled or unscheduled visit after Randomization has an increase of ≥ 500 cells/ μ L above the Screening value, another CBC with differential must be performed before the next dose. It is recommended to perform the CBC with differential close to the next dosing day and at least 10 days after the prior dose.
- If AEC is >1000 cells/ μ L, a CBC with differential may be repeated the day before the dosing day or on the dosing day, prior to administration of study intervention.
- If AEC remains >1000 cells/ μ L, study intervention should be interrupted. Study intervention may be restarted once AEC is ≤ 1000 cells/ μ L.

Hypereosinophilic syndrome and eosinophil-associated organ injury are described in Appendix 9.

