Antioxidants (eg, polypodium leucotomas, superoxide dismutase, alpha-lipoic acid, Ginko Biloba)	No newly initiated 3 month prior to Randomization, and the dose should remain stable during the study duration
Other topical treatments or any procedures (eg, needling) that could affect vitiligo	4 weeks (or 5-drug half-lives)
Systemic or topical non-biologic immunomodulators/immunosuppressants (eg, corticosteroids, calcineurin inhibitors, tacrolimus/pimecrolimus)	4 weeks for systemic, and 2 weeks for topical
Any kind of phototherapy (eg, UV/UVB phototherapy, PUVA therapy, tanning beds, laser therapy)	4 weeks
Any other prescription or over-the-counter medication, traditional Chinese medicine, herbal supplement, or other therapy used to treat vitiligo	4 weeks
Other Therapies	
Any investigational drug	4 weeks or 5 half-lives of the investigational drug (whichever is longer)
Live vaccines Note: JYNNEOS for prevention of smallpox and mpox, (also known as monkeypox disease) is allowed. JYNNEOS is a live, non-replicating vaccine. See Appendix 8 for examples of live and non-live vaccines.	4 weeks (or longer if required locally)
CTLA-4=cytotoxic T-lymphocyte-associated protein 4; JAK=Janus kinase; IL-2=interleukin 2; NSAIDs= nonsteroidal anti-inflammatory drugs; PD-1= programmed cell death protein 1; PDE4= phosphodiesterase-4 enzyme; PD-L 1= programmed cell death ligand 1; PUVA=psoralen and ultraviolet rays A; S1P= sphingosine 1 phosphate; TYK2= tyrosine kinase 2; UV/UVB=ultraviolet/ultraviolet rays B. ^a Medication use is prohibited until the last dose of study intervention is administered (study completion or early discontinuation).	

See Appendix 7 for country-specific requirements.

Prior/Concurrent Clinical Study Experience

20. Has participated in another investigational clinical study within 4 weeks (see [Table 1](#) for prohibited period) prior to Randomization

Diagnostic Assessments

21. Has Screening laboratory test results within the following parameters:

- Hemoglobin <8.5 g/dL
- WBC < $3.5 \times 10^3/\mu\text{L}$
- Absolute neutrophil count < $1.5 \times 10^3/\mu\text{L}$
- Absolute lymphocyte count < $0.5 \times 10^3/\mu\text{L}$
- Absolute eosinophil count >1000 cells/ μL
- Absolute platelet count < $100 \times 10^3/\mu\text{L}$
- >2.0 X ULN of any of the following: ALT, AST, ALP, or >ULN total bilirubin (1.5 X ULN total bilirubin if known Gilbert's syndrome)
- eGFR $\leq 30 \text{ mL/min/1.73 m}^2$, based on the MDRD equation

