7 DISCONTINUATION OF STUDY INTERVENTION AND PARTICIPANT WITHDRAWAL

7.1 Discontinuation of Study Intervention

Discontinuation of study intervention does not represent withdrawal from the study.

As certain data on clinical events beyond study intervention discontinuation may be important to the study, they must be collected through the participant's last scheduled follow-up, even if the participant has discontinued study intervention. Therefore, all participants who discontinue study intervention before completion of the protocol-specified treatment period will still continue to be monitored in the study and participate in the study visits and procedures as specified in Section 1.3 and Section 8.10.5 unless the participant has withdrawn from the study (Section 7.2).

Participants may discontinue study intervention at any time for any reason or be discontinued from the study intervention at the discretion of the investigator should any untoward effect occur. In addition, a participant may be discontinued from study intervention by the investigator or the Sponsor if study intervention is inappropriate, the study plan is violated, or for administrative and/or other safety reasons.

A participant must be discontinued from study intervention, but continue to be monitored in the study for any of the following reasons:

- The participant or participant's legally acceptable representative requests to discontinue study intervention.
- The participant's treatment assignment has been unblinded by the investigator, MSD subsidiary, or through the emergency unblinding call center.
- The participant has a medical condition or personal circumstance, which, in the opinion of the investigator and/or Sponsor, places the participant at unnecessary risk from continued administration of study intervention.
- The participant has a confirmed positive serum pregnancy test.
- The participant has AEC >1500 cells/ μ L and has confirmed or suspected hypereosinophilic syndrome or eosinophil-associated organ injury; see Appendix 9 for details.
- The participant has a persistent moderate increase in eosinophils for ≥ 8 weeks, defined as AEC ≥ 1500 cells/ μ L on at least 3 consecutive tests. The interval between the tests should be at least 1 week.
- The participant has AEC >5000 cells/ μ L at a single time point.
- The participant develops active or latent TB.
- The participant has an SAE of infection (eg, sepsis), which cannot be adequately controlled by anti-infective treatment.

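### For screening eosinophil counts above 650, protocol 6.6.3 triggers the retest on a relative rise but interrupts on an absolute 1000; read in sequence, counts needing no retest exceed counts that interrupt

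*Protocol*

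**What the plan says.** Protocol 6.6.3 has two branches, each of three bullets.

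In the branch for a screening AEC of 650 cells/µL or less, everything uses one number. A count above 1000 requires a repeat before the next dose. The second bullet, "If AEC is still >1000 cells"/µL, allows a further repeat. A count that stays above 1000 interrupts dosing, and dosing may resume at 1000 or below.

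The other branch begins "For participants with AEC >650 cells"/µL at Screening. Its bullets are:

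- Bullet 1: "If AEC at a scheduled or unscheduled visit after Randomization has an increase of" at least 500 cells/µL "above the Screening value, another CBC with differential must be performed before the next dose".
- Bullet 2: if AEC is above 1000, the count may be repeated the day before dosing or on the dosing day. The word *still*, used in the other branch, is absent.
- Bullet 3: "If AEC remains >1000 cells"/µL, "study intervention should be interrupted. Study intervention may be restarted once AEC is" 1000 or below.

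Exclusion criterion 21 in section 5.2 lists "Absolute eosinophil count >1000 cells"/µL at Screening, so this second branch covers screening values from 651 to 1000.

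**The concern.** In this branch the step that opens the procedure is measured from the participant's own baseline, and the steps that close it are measured on a fixed scale. The opening level is always the higher of the two. A participant can therefore sit above the interruption level without the procedure starting, and can be interrupted at a lower count once it has started.

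Protocol 2.3 lists raised eosinophils among the most frequently reported adverse events with MK-6194, and 4.2.1.2 presents eosinophil monitoring as a specific safety measure. Protocol 8.5 also sends overdose cases to 6.6.3. If the text supports two readings, two sites acting in good faith can treat the same counts differently.

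**Working it through.** No sample size, power or alpha figure is involved, so there is no plan figure to reproduce. The check applies the written bullets to whole-number counts.

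**Inputs.** Screening value S = 651 to 1000 (6.6.3 branch heading; exclusion criterion 21). Required rise: 500 (6.6.3, bullet 1). Interruption above 1000 and restart at 1000 or below (6.6.3, bullet 3).

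**Reading A: bullets 2 and 3 apply only after bullet 1.** The retest trigger is T = S + 500. The highest count with no required retest is T − 1 = S + 499. The lowest confirmed count that interrupts, once triggered, is 1001.

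| Screening S | Trigger S + 500 | Counts above 1000 with no retest required by 6.6.3 | Lowest confirmed count that interrupts |
|---|---|---|---|
| 651 | 1151 | 1001–1150 | 1001 |
| 700 | 1200 | 1001–1199 | 1001 |
| 800 | 1300 | 1001–1299 | 1001 |
| 900 | 1400 | 1001–1399 | 1001 |
| 1000 | 1500 | 1001–1499 | 1001 |

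The inversion occurs whenever S + 499 > 1001, that is S > 502. It therefore holds at all 1000 − 651 + 1 = 350 whole-number screening values in the branch. At S = 650 the other branch applies and there is no such band.

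Two worked paths:

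- Same participant, S = 800. A count of 1299 is a rise of 499, so no retest is required. A count of 1300 is a rise of 500, so a retest is required; if repeats stay at 1001, dosing is interrupted.
- Two participants. S = 1000 with 1499 (rise 499): no retest. S = 700 with 1200 (rise 500) and repeats of 1001: interrupted.

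**Reading B: bullet 2 stands alone.** Any count above 1000 may be repeated, and any that remains above 1000 interrupts. The inversion disappears. But S + 500 is at least 1151, so bullet 1 never reaches a count that bullet 2 does not already cover. All it adds is to make an optional repeat compulsory from S + 500 upward.

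**The readings compared.** Take S = 800 and a sustained count of 1250. Under A, the rise is 450, no retest is required and dosing continues. Under B, a site that repeats the count and finds 1250 again interrupts.

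**Other eosinophil rules.** In 7.1, one discontinuation rule is "The participant has a persistent moderate increase in eosinophils for" 8 weeks or more, defined as at least 1500 on at least three consecutive tests. The others need more than 1500 with confirmed or suspected organ injury or hypereosinophilic syndrome, or a single value above 5000. The eosinophil events of clinical interest in 8.4.7 need more than 5000, or more than 1500 with such injury or syndrome. None acts on 1001–1499.

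**Time to the next scheduled count.** Hematology falls at Weeks 2, 4, 8, 12, 18, 24, 26, 28, 32, 36, 44 and 52. From Week 12 to 24 the gap is 6 weeks, and from Week 36 to 52 it is 8. With injections every 2 weeks, those due at Weeks 38, 40 and 42 fall between the Week 36 and Week 44 counts.

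**The case against.** The strongest defence is that a high trigger with a lower clearance level may be deliberate. The two counts are also not taken under identical conditions: the retest is recommended close to the next dose and at least 10 days after the last one, while the first count may have been taken nearer a dose. This is possible, but the protocol states no such intent. It also does not account for a sustained count between 1001 and S + 499, which never starts the procedure on Reading A.

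Several other points stand and limit the finding:

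- The inversion depends on Reading A. The words for a further test, a repeat and a count that remains high, and the parallel with the other branch, favour that reading. The missing *still* leaves B open.
- A reader might infer that on B the relative trigger does nothing. That is too strong, since bullet 1 is compulsory and bullet 2 is not.
- A reader might infer that restart at 1000 or below is itself an error. It matches the entry limit.
- A step at 650/651, and a band that widens with baseline, come with any cut-point and any baseline-relative trigger. They are not separate faults.
- A reader might infer that counts in the band go unmanaged. They do not: hematology is scheduled, every laboratory report must be reviewed, repeats are sought for values judged clinically significantly abnormal (8.3.4), and the investigator may stop treatment (7.1). The accurate statement is that 6.6.3 requires no retest before the next dose.
- Section 2.3 describes the increases seen so far as transient and mild to moderate, with no eosinophil-associated organ injury.

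**Conclusion.** The inconsistency is real and sits in a stated safety rule. On the more natural sequential reading, participants screened at 651–1000 have a band from 1001 to screening plus 499 in which 6.6.3 asks for no retest before the next dose, although confirmed counts as low as 1001 interrupt once the trigger has been met. On the stand-alone reading the fault is smaller: a trigger that is largely redundant, and wording that lets sites diverge.

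A reader might go further and infer that uneven interruptions would distort the comparison of regimens. The documents do not support that. They give neither the share of participants screened at 651–1000 nor an interruption rate, and 6.4 requires consultation with the sponsor when two or more consecutive injections are interrupted, which limits divergence between sites. Any effect on exposure is unquantified, and primary power and alpha are unaffected. The point should be corrected as a matter of safety conduct, not as a threat to the primary analysis.

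**What to change.** The sponsor's medical team should reconcile the trigger, interruption and restart statements in the branch of 6.6.3 for screening AEC above 650, and state whether bullets 2 and 3 apply only after bullet 1 has been met. If the difference between the relative trigger and the absolute level is intended, the protocol should say so. No threshold or rule structure is proposed here; that is a clinical decision.

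The cost is an amendment to three bullets and a memo to sites. Depending on how the text is reconciled, some additional pre-dose blood counts may be needed, so a cost of zero in testing cannot be promised.
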